4.3 Study Visits and Procedures

4.3.1 Visit 1 (Day 1) - Enrollment and Vaccination

- Obtain parent(s) or legal guardian(s) permission by written informed consent prior to performing any study procedures.
- Obtain child assent if applicable to site
- May read script about study to participants aged 5 to 6 years if applicable to site
- Medical history and medication history will be obtained, including a review of all current medications and medications taken within 28 days prior to enrollment.
- A targeted physical exam may be performed by clinical study staff, based on information gathered during medical history
- History of asthma and allergy disease
- Temperature will be recorded prior to immunization; oral temperature must be <100.4° F without use of antipyretic medication prior to administration of vaccine.

- Sex, height, weight, and BMI (demographics)
- Eligibility criteria will be reviewed to determine if child meets criteria for study.
- A urine or serum pregnancy test will be collected on post-menarchal females.
- For females, parent(s) or legal guardian(s) will be asked whether their child has had onset of menarche. If the answer is "yes", a urine or serum pregnancy test will be performed as part of eligibility assessment, and conducted within 24 hours before vaccination. Results of a positive pregnancy test would be communicated with the female being tested in accordance with local institutional practices.
- Asthma severity will be assessed according to Table 2, section 4.4.
- Asthma control will be assessed with following tools:
 - Administration of the Childhood Asthma Control Test (c-ACT) or Asthma Control Test (ACT) score, as appropriate by age (Appendix, Fig. A1)
 - Clinical assessment to assess baseline asthma clinical symptoms [Preventative Omalizumab or Step-up Therapy for Severe Fall Exacerbations (PROSE) asthma symptom questionnaire] (Appendix Figure A2)
- Patient and parent(s) or legal guardian(s) will be taught proper peak flow technique and will be provided with a digital peak flow meter by the study staff, even if they have another peak flow meter at home. A baseline peak flow measurement (standing, three attempts) will be collected. The patient (and parent(s) or legal guardian(s)) will be requested to use this same peak flow meter every day at home beginning on the day of vaccination and for 14 days following vaccination, (days 1 through 15). (see section 4.6 below)

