4.8 Monitoring Vaccine Safety in the First 15 Days

On the vaccination day and for the next 14 days post-vaccination (until day 15), all participants will be monitored daily by their parent(s) or legal guardian(s) and the information will be recorded using memory aids provided at the enrollment visit. Daily reactogenicity, including measurement of nighttime awakening, and unscheduled albuterol use and two validated questionnaires will be completed (c-ACT/ACT and PROSE). PROSE will be assessed at baseline (Day 1) and on Day 15.

In addition to the two questionnaires above, several predefined events that could occur after vaccine administration will also be recorded for 14 days after vaccination (through day 15). These will include fever (oral temperature $\geq 100.4^{\circ}$ F), asthma symptoms, and other respiratory and systemic symptoms. Medication receipt, new prescriptions for asthma medications, and any previously unscheduled healthcare utilization (medical office visits, ED visits, hospitalizations) will also be documented on the reaction form. To ensure compliance with the reaction assessment, parents will be called, emailed through REDCap, or receive text messages on Days 4, 8 and 15 by the study staff.

On the day of vaccination and during the first 14 days (until day 15) after vaccination, if the participant reports an increase in their symptoms and an increase in the need for medications for their asthma, the family will be instructed to contact the study staff, so medical records can later be collected, if needed. If at any point a study participant is experiencing symptoms of any asthma exacerbation, the participant or their parent will be instructed to contact their primary care provider (PCP) and inform study staff of this encounter.

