13.1 Figure A1. Childhood Asthma Control Test (c-ACT)

Patient Name:

Patient ID#:

Primary Care Provider:

Childhood Asthma Control Test for children 4 to 11 years.

Date:

[figure not shown]
How to take the Childhood Asthma Control Test

- Step 1 Let your child respond to the first four questions (1 to 4). If your child needs help reading or understanding the question, you may help, but let your child select the response. Complete the remaining three questions (5 to 7) on your own and without letting your child's response influence your answers. There are no right or wrong answers.
- Step 2 Write the number of each answer in the score box provided.
- Step 3 Add up each score box for the total.
- Step 4 Take the test to the doctor to talk about your child's total score.

If your child's score is 19 or less, it may be a sign that your child's asthma is not controlled as well as it could be. No matter what the score, bring this test to your doctor to talk about your child's results.

Have your child complete these questions. 1. How is your asthma today?

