3.3 Exploratory

EOM 1.1: Proportion of participants with asthma exacerbations by asthma severity group (Mild vs. Moderate-Severe) during the 14 days after receipt of LAIV4 or IIV4

EOM 1.2: Proportion of participants with asthma exacerbations by asthma severity group (Mild vs. Moderate-Severe) during the 42 days after receipt of LAIV4 or IIV4

EOM 2.1: Proportion of participants with asthma symptoms of cough by asthma severity group (Mild vs. Moderate-Severe) during the 14 days after receipt of LAIV4 or IIV4

EOM 2.2: Proportion of participants with asthma symptoms of wheezing by asthma severity group (Mild vs. Moderate-Severe) during the 14 days after receipt of LAIV4 or IIV4

EOM 2.3: Proportion of participants with asthma symptoms of tightness in chest by asthma severity group (Mild vs. Moderate-Severe) during the 14 days after receipt of LAIV4 or IIV4

EOM 2.4: Proportion of participants with asthma symptoms of nighttime awakening by asthma severity group (Mild vs. Moderate-Severe) during the 14 days after receipt of LAIV4 or IIV4

EOM 2.5: Proportion of participants with unscheduled albuterol use to treat asthma symptoms by asthma severity group (Mild vs. Moderate-Severe) during the 14 days after receipt of LAIV4 or IIV4

EOM 3.1: Proportion of participants that experience a clinically significant decrease in Peak Flow measurement during the 14 days after vaccination with LAIV4 or IIV4, by asthma severity group (Mild vs. Moderate-Severe)

Note: A clinically significant decrease in peak flow is defined as a decrease of $\geq 20\%$ in PEFr from baseline PEFr.

EOM 4.1: Numerical changes in Peak Flow when compared to baseline during the 14 days after LAIV4 vs IIV4, by asthma severity group (Mild vs. Moderate-Severe)

EOM 4.2: Description of changes in Peak Flow when compared to baseline during the 14 days after LAIV4 vs IIV4, by asthma severity group (Mild vs. Moderate-Severe)

EOM 5.1 Changes in Childhood Asthma Control Test (cACT) scores (participants aged 5-11 years) or Asthma Control Test (ACT) scores (participants aged 12-17 years) from baseline during the 42 days after LAIV4 or IIV4, by asthma severity group (Mild vs. Moderate-Severe)

EOM 6.1: Maximum number of asthma symptom days using Preventative Omalizumab or Step-up Therapy for Severe Fall Exacerbations (PROSE) from baseline during the 14 days after vaccination with LAIV4 or IIV4, by asthma severity group (Mild vs. Moderate-Severe)

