The numerical changes of c-ACT and ACT from the baseline during the 14 days post-vaccination will be graphed and compared by asthma severity group using either t-test or Wilcoxon rank-sum test. We may categorize c-ACT and ACT into

well-controlled, poorly controlled, and very poorly controlled groups and run Mantel-Haenszel Chi-square test by treatment and asthma severity groups.

- f) The sixth exploratory objective (EO 6) is to compare asthma symptom days using Preventative Omalizumab or Step-up Therapy for Severe Fall Exacerbations (PROSE) from baseline during the 14 days after vaccination by asthma severity group (Mild vs. Moderate-Severe).

The numerical changes of PROSE from the baseline during the 14 days post-vaccination will be graphed and compared by asthma severity group using either t-test or Wilcoxon rank-sum test.

- g) The seventh exploratory objective (EO 7) is to compare rates of medical utilization for asthma-related symptoms during the 14 and 42 days after LAIV4 or IIV4, by asthma severity group.

Two Mantel-Haenszel Chi-square tests will be used to compare rates of medical utilization for asthma-related symptoms by treatment and asthma severity groups at 14 and 42 days after receipt of LAIV4 or IIV4, respectively.

- h) The eighth exploratory objective (EO 8) is to describe and compare reactogenicity events during the 14 days after receipt of LAIV4 or IIV4, by asthma severity group. Reactogenicity will be assessed by grading on a 0-3 scale, with 0 being used for no events, grade 1 (mild), grade 2 (moderate), and grade 3 (severe).

Reactogenicity is assessed by:

1. Runny nose/nasal congestion
2. Sore throat
3. Chills
4. Earache/ear pain
5. Headache
6. Muscle aches/sore muscles
7. Bone/joint pain
8. Decreased activity/lethargy/fatigue
9. Rash/hives
10. Stomach pain
11. Nausea/vomiting

These events will be graded based on the following scale

1. Grade 0: Symptom did not occur
2. Grade 1: Noticed a change but does not interfere with things done on a normal day
3. Grade 2: Interferes with activity but did not require a doctor's office visit or missed day of school/daycare
4. Grade 3: Prevents daily activity and/or required a doctor's office visit and/or missed day of school/daycare

Fever will be assessed by the following grading scale

1. Grade 0: <100.4 °F
2. Grade 1: 100.4 – 100.9 °F
3. Grade 2: 101 – 102.1 °F
4. Grade 3: >102.1 °F

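### EO5 and EO6 compare raw change scores with no baseline covariate; for the randomised LAIV4 vs IIV4 contrast, a baseline-adjusted model would be at least as precise, at no data cost

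*SAP*

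**What the plan says.** For EO5, SAP 8.3 e) says "The numerical changes of c-ACT and ACT from the baseline during the 14 days post-vaccination will be graphed and compared". For EO6, SAP 8.3 f) says "The numerical changes of PROSE from the baseline during the 14 days post-vaccination will be graphed and compared". Both sentences continue in the same way: "compared by asthma severity group using either t-test or Wilcoxon rank-sum test". Neither names a covariate, a regression model or an adjusted estimate.

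EO5 has an optional second analysis ("We may categorize c-ACT and ACT into" three levels of control), a Mantel-Haenszel test by treatment and severity. The baseline score does not enter that either.

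Protocol 8.2 leaves covariate adjustment to the SAP. SAP 5.2 says that exploratory objectives are not stratified by site, and the SAP gives no other adjustment for EO5 or EO6.

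The baselines are in hand. Protocol 4.3.1 schedules "Administration of the Childhood Asthma Control Test (c-ACT) or Asthma Control Test (ACT) score, as appropriate by age" at Visit 1, and Protocol 4.8 says "PROSE will be assessed at baseline (Day 1) and on Day 15". Protocol Table 1 places the follow-up c-ACT/ACT at Visit 6 (Day 43). The declared EO6 measure in SAP 3.3 begins "EOM 6.1: Maximum number of asthma symptom days using Preventative Omalizumab or Step-up Therapy for Severe Fall Exacerbations (PROSE) from baseline".

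**The concern.** A change score fixes the coefficient of the baseline score at 1. That is the best choice only if the regression of follow-up on baseline really has slope 1. PROSE items 1 to 5 count days or nights out of 14, so a child who starts at 0 cannot improve and a child who starts at 14 cannot worsen. With such bounds the change tends to depend on where the child started. Subtraction then over-corrects for any chance difference in baseline between the arms.

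At stake is the precision of two exploratory, parent- or child-reported comparisons of asthma control and symptoms after the two vaccines. Intervals would be wider than the collected data allow, and a chance baseline difference could shift the estimate.

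**Working it through.** **The plan's own figures.** The documents give no SD, correlation, effect size or power for EO5 or EO6. The only power figure belongs to the primary endpoint (SAP 4.2: 135 per arm, 12% in both arms, margin 10%, one-sided 5%). It reproduces: Φ(0.10/√(2 × 0.12 × 0.88/135) − 1.645) = Φ(0.883) = 81.1%. Nothing below touches it.

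**Inputs.** n = 135 per arm (SAP 4.2). Assumed, not in the documents: r, the correlation between baseline and follow-up score, and k, the follow-up SD divided by the baseline SD.

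**Equal SDs (k = 1, common SD s), LAIV4 vs IIV4.**
- Variance of the difference in mean change: (2/n) × 2s²(1 − r).
- Large-sample variance of the baseline-adjusted difference: (2/n) × s²(1 − r²).
- Ratio, adjusted to change: (1 − r²)/[2(1 − r)] = (1 + r)/2. Information lost by the change score: (1 − r)/2.

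| r | Loss | Adjusted-analysis equivalent of 270 children, 270(1 + r)/2 |
|---|---|---|
| 0.2 | 40% | 162 |
| 0.3 | 35% | 175.5 |
| 0.5 | 25% | 202.5 |
| 0.7 | 15% | 229.5 |
| 0.9 | 5% | 256.5 |

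**Smallest difference detectable with 80% power, two-sided 5%.** The base value is (1.960 + 0.842) × √(2/135) = 0.341 SD. Multiply by √[2(1 − r)] for the change score and by √(1 − r²) for the adjusted model.
- r = 0.3: 0.403 vs 0.325 SD.
- r = 0.5: 0.341 vs 0.295 SD.
- r = 0.7: 0.264 vs 0.244 SD.

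These use all 135 per arm. A separate fit for each questionnaire has fewer children.

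**Unequal SDs.** Loss = 1 − k²(1 − r²)/(1 + k² − 2rk).

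| k | r = 0.3 | r = 0.5 | r = 0.7 |
|---|---|---|---|
| 0.8 | 50% | 43% | 37% |
| 1 | 35% | 25% | 15% |
| 1.25 | 22% | 11% | 2% |

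**Direction.** The same expression can be written (1 − rk)²/(1 + k² − 2rk). The numerator is a square, so the loss is never negative. It is zero only when rk, the slope of follow-up on baseline, equals 1.

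**Imbalance.** The change-score estimate is the follow-up difference minus the baseline difference. The adjusted estimate is the follow-up difference minus rk times the baseline difference. They differ by (1 − rk) times the baseline difference. At r = 0.5 and k = 1, half of any chance baseline difference passes into the change-score result with its sign reversed.

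**Which contrast, and which day.** The EO5 and EO6 test sentences refer to severity groups. SAP 8.3 d) (EO4) has an extra sentence comparing the two treatment groups; e) and f) have none. For EO5, the test sentence uses 14 days, while the objective that it serves uses 42 days and Table 1 collects c-ACT/ACT only at Visits 1 and 6.

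**The case against.** The strongest reply is that this is a choice of method and not an error. A change score does use the baseline. Under randomisation it gives an unbiased vaccine contrast with no type I error problem. Permuted blocks by site, by severity and (in the second season) by age group limit some imbalance. EO5 and EO6 are two of ten exploratory objectives with no power claim. All of that stands. What remains is that the planned method is in general less precise than one that uses data already collected.

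Four stronger readings are tempting, and the documents do not support them.

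- **The loss is a known 15–35%.** That range needs r between 0.3 and 0.7 and equal SDs, neither of which is documented.
- **The gain holds whichever groups are compared.** It holds for LAIV4 vs IIV4. If the contrast is mild vs moderate-severe, as the wording permits, the groups are not randomised. Conditioning on baseline then changes what is estimated and is not a free gain in precision.
- **c-ACT and ACT changes are to be pooled, or a different PROSE endpoint is to be tested.** The SAP never says that the two questionnaires are pooled; it assigns each to its own age group and is silent on how they are analysed. On PROSE, the EO6 lead sentence names symptom days, so the test sentence is loose shorthand.
- **This is the main patient-reported evidence.** Secondary objective SO2 (cough, wheeze, chest tightness, night waking and albuterol use from the memory aid) ranks above it.

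**Conclusion.** The point holds as an optional improvement to two exploratory analyses. SAP 8.3 e) and f) specify unadjusted tests of raw change although both baselines are collected at Visit 1. For the 1:1 randomised vaccine contrast, adding the baseline score costs no large-sample precision and usually gains some.

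The direction is secure; the size is not. With equal SDs the loss runs from 40% at r = 0.2 to 5% at r = 0.9. For r from 0.3 to 0.7 it is 37–50% if the follow-up SD is 0.8 times baseline and 2–22% if it is 1.25 times. The formulas concern means, so they are only approximate for the Wilcoxon option or for heavily tied scores. The primary and secondary conclusions do not change.

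**What to change.** Reword SAP 8.3 e) and f):

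1. State the contrast as LAIV4 minus IIV4, overall and within each severity group.
2. Estimate it, with a 95% CI, from a model of the follow-up score on vaccine, baseline score, severity and vaccine × severity. Use an ordinal model if the scores are heavily tied. Say how the overall difference is formed, for example by weighting the two severity-specific differences by group size, because the vaccine coefficient alone refers to one severity group.
3. For EO5, reconcile the 14-day wording with the 42-day objective and the Visit 6 schedule, and take the Day 43 score as the outcome. Fit c-ACT and ACT each within its own age group.
4. For EO6, take the Day 15 maximum symptom days named in EOM 6.1, with the Day 1 value as the covariate, and say which PROSE items enter the maximum.

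The cost is SAP text and programming only. No new data, visit or sample size is needed.

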Nearly 70% of children were on inhaled corticosteroids. No significant differences were reported between the LAIV and TIV vaccine recipients in the incidence of asthma exacerbations (during 42 days after vaccination), mean peak expiratory flow rates, asthma symptom scores, or nighttime awakening scores. Rhinorrhea and nasal congestion were commonly reported symptoms among recipients of LAIV during the 15 days after study vaccination; injection site reactions were the most commonly reported symptoms among recipients of TIV. Overall, there was no evidence of a significant increase in adverse pulmonary outcomes for LAIV compared with TIV. LAIV had a significantly greater relative efficacy of 35% compared with TIV in this high-risk population.⁴ This well designed and conducted clinical trial serves as a model for the conduct of the proposed trial.

More recently, the Centers for Disease Control and Prevention's Vaccine Safety Datalink published a study assessing the safety of LAIV in persons with asthma.¹⁹ They assessed medically-attended respiratory events during the 14 days after LAIV (trivalent LAIV and monovalent 2009 H1N1 pandemic LAIV) compared with the 29 to 42 days after vaccination among persons 2 through 49 years over three influenza seasons (2008-2009; 2009-2010; 2010-2011). Most patients had intermittent or mild persistent asthma. Medically-attended upper or lower respiratory events (outpatient or inpatient) were not significantly increased after LAIV. This was true for younger children 2-8 years as well as older children 9-17 years.

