5.1.2 Live, attenuated influenza vaccine (LAIV)

ACIP considers use of LAIV as a precaution for children aged \geq 5 years with asthma.¹ In addition to the usual risks as described in the VIS (https://www.cdc.gov/vaccines/hcp/vis/current-vis.html), children with asthma might experience higher rates of asthma exacerbations after LAIV than with IIV.^{9,11,20} Most people who get LAIV do not have any problems with it. Reactions to LAIV may resemble a very mild case of flu. Some of the most common symptoms that have been reported following LAIV in children and adolescents 2-17 years of age are runny nose, nasal congestion, sore throat, cough, fever, headache, muscle aches, wheezing, abdominal pain, vomiting, or diarrhea.¹⁰

There is also the potential risk of loss of confidentiality about the information obtained as part of this study (see section 9).

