2.3 Exploratory

EO 1: To compare the proportions of participants with asthma exacerbations during the 14 and 42 days after receipt of LAIV4 or IIV4, by asthma severity group (Appendix 1).

EO 2: To compare the proportion of participants with asthma symptoms and unscheduled albuterol use during the 14 days after receipt of LAIV4 or IIV4, by asthma severity group.

EO 3: To compare the proportion of participants who experience a clinically significant decrease in PEFR from baseline during the 14 days after receipt of LAIV4 or IIV4, by asthma severity group.

EO 4: To describe and compare changes in Peak Expiratory Flow Rate (PEFR) from baseline (pre-vaccination) PEFR after vaccination over time during the 14 days after receipt of LAIV4 or IIV4, by asthma severity group.

EO 5: To compare change in Childhood Asthma Control Test (c-ACT) score (participants aged 5-11 years) or Asthma Control Test (ACT) score (participants aged 12-17 years) from baseline through 42 days after LAIV4 or IIV4, by asthma severity group

EO 6: To compare asthma symptom days using Preventative Omalizumab or Step-up Therapy for Severe Fall Exacerbations (PROSE) from baseline during the 14 days after vaccination by asthma severity group.

EO 7: To compare rates of medical utilization for asthma-related symptoms during the 14 and 42 days after LAIV4 or IIV4, by asthma severity group.

EO 8: To describe and compare systemic reactogenicity events during the 14 days after receipt of LAIV4 or IIV4, by asthma severity group.

EO 9: To describe and compare serious adverse events after LAIV4 vs. IIV4 during the 42 days after vaccination and assess relatedness to vaccine.

EO 10: To describe and compare asthma symptoms and control among participants with and without a history of allergic rhinitis or hay fever, used as a proxy for allergic versus non-allergic asthma.

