EOM 7.1: Rates of medical utilization for asthma-related symptoms during the 14 days after LAIV or IIV4 by asthma severity group (Mild vs. Moderate-Severe)

EOM 7.2: Rates of medical utilization for asthma-related symptoms during the 42 days after LAIV or IIV4 by asthma severity group (Mild vs. Moderate-Severe)

EOM 8.1: Description and comparison of systemic reactogenicity events during the 14 days after LAIV or IIV4 by asthma severity group (Mild vs. Moderate-Severe)

a. Proportions of systemic reactogenicity events during the 14 days after LAIV or IIV4 by asthma severity group

EOM 9.1: Description and comparison of serious adverse events during the 42 days after IIV4 or LAIV4 and performance of a relatedness assessment

a. Proportions of serious adverse events during the 42 days after IIV4 or LAIV4 and performance of a relatedness assessment

EOM 10.1: Description and comparison of asthma symptoms and asthma control (PROSE, and c-ACT/ACT scores) among participants with and without a history of allergic rhinitis or hay fever, as a proxy for allergic versus non-allergic asthma during the 42 days after IIV4 or LAIV4

- a. *Proportions of asthma symptoms and asthma control (PROSE, and c-ACT/ACT scores) among participants with and without a history of allergic rhinitis or hay fever, as a proxy for allergic versus non-allergic asthma during the 42 days after IIV4 or LAIV4*

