For each reactogenicity reaction, summary statistics will be performed such as frequencies and percentages for categorical variables and mean/standard deviation or median/interquartile range for continuous variables. Results will be presented as none, mild, moderate and/or severe reactions. There will be statistical comparisons among moderate/severe reactogenicity reactions by treatment groups and asthma severity groups (Mild vs. Moderate-Severe) using Mantel-Haenszel tests.

- i) The ninth exploratory objective (EO 9) is to describe and compare serious adverse events during the 42 days after LAIV4 or IIV4 and assess relatedness to vaccine

For each serious adverse event and assessing relatedness, summary statistics will be performed such as frequencies and percentages for categorical variables and mean/standard deviation or median/interquartile range for continuous variables. The Mantel-Haenszel test will be used for comparisons of proportions of having at least one SAE by treatment groups and asthma severity levels. Listing of the serious adverse events by study LAIV4 or IIV4 groups will also be presented.

- j) The tenth exploratory objective (EO 10) is to describe and compare asthma symptoms and asthma control (PROSE, and c-ACT/ACT scores) among participants with and without a history of allergic rhinitis or hay fever, as a proxy for allergic versus non-allergic asthma.

For each asthma symptom and control, summary statistics will be performed such as frequencies and percentages for categorical variables and mean/standard deviation or median/interquartile range for continuous variables. The Mantel-Haenszel test will be used for comparisons of proportions of having at least one symptom by treatment groups and allergic asthma status (history of allergy rhinitis or hay fever vs. no history of these conditions).

No adjustments will be made to the alpha level (two-sided alpha=0.05) for these exploratory objective analyses.

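### EO8 records and tabulates reactogenicity at every grade but formally tests only moderate/severe reactions, so an LAIV4 excess confined to mild reactions is outside the planned test

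*SAP*

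**What the plan says.** The EO8 objective in SAP 2.3 is "To describe and compare systemic reactogenicity events during the 14 days after receipt of LAIV4 or IIV4, by asthma severity group". The outcome measure EOM 8.1a in SAP 3.3 is "Proportions of systemic reactogenicity events during the 14 days after LAIV or IIV4 by asthma severity group". Neither is limited to a grade.

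SAP 8.3 h sets the scale: "Reactogenicity will be assessed by grading on a 0-3 scale, with 0 being used for no events". It covers 11 listed symptoms, the first being runny nose/nasal congestion, and fever is graded separately on temperature. The mild level is defined as "Grade 1: Noticed a change but does not interfere with things done on a normal day".

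For reporting, SAP 8.3 h states "Results will be presented as none, mild, moderate and/or severe reactions". For testing it states "There will be statistical comparisons among moderate/severe reactogenicity reactions by treatment groups and asthma severity groups", by Mantel-Haenszel tests at an unadjusted two-sided 0.05. No other test of these 12 items is planned.

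On what to expect after LAIV, Protocol 5.1.2 says "Reactions to LAIV may resemble a very mild case of flu". Protocol 1, describing the asthma trial it takes as its model, says "Rhinorrhea and nasal congestion were commonly reported symptoms among recipients of LAIV during the 15 days after study vaccination".

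**The concern.** The objective is to describe and compare events, and the outcome measure counts events of any grade, yet the inferential comparison begins at grade 2. On the natural reading, a child with a mild reaction is counted with a child who had none. The protocol's own account of LAIV points to mild and nasal effects, so the effect it most leads one to expect lies largely below the cut. No reason for the cut is given. The asthma symptoms in SO2 and EO2, by contrast, are compared as yes/no with no severity threshold.

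At stake is how an EO8 result is read. A non-significant result could be taken to cover reactogenicity as a whole when only grades 2 and 3 were tested.

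**Working it through.** **1. The plan's own figure.** SAP 4.2 gives 135 per arm, 12% in both arms, a 10-point margin, one-sided 0.05, and 81.1% power for the primary test. Check: standard error = √(2 × 0.12 × 0.88 / 135) = 0.0396, and power = Φ(0.10/0.0396 − 1.645) = Φ(0.883) = 81.1%. It reproduces. No power, rate or grade distribution is stated for EO8. Only the 135 per arm carries over.

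**2. Assumptions for EO8.** 135 per arm; two asthma-severity strata of about equal size with the same grade distribution; two-sided 0.05; one worst grade per child per item. IIV4 distributions (none/mild/moderate/severe) are assumed:
- Set 1: 75/17/6/2%, 60/28/9/3%, 50/33/13/4%.
- Set 2: 70/20/8/2%, 55/30/12/3%, 40/40/15/5%.

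**3. Closed-form check, IIV4 = 60/28/9/3%.** For two proportions p1 and p2 with mean p̄ and difference d, power ≈ Φ{[d − 1.96√(2p̄(1−p̄)/135)] / √[(p1(1−p1)+p2(1−p2))/135]}.
- *15 points added to mild only.* LAIV4 becomes 45/43/9/3%. Grade 2 or higher is 12% in both arms, so the planned test rejects at its alpha, 5%. Any grade is 40% v 55%: Φ[(0.15 − 1.96 × 0.0608)/0.0601] = Φ(0.51) ≈ 70%.
- *Common odds ratio 1.8.* Grade 2 or higher: odds 0.12/0.88 × 1.8 = 0.245, so 12% v 19.7%. Φ[(0.077 − 1.96 × 0.0445)/0.0442] = Φ(−0.23) ≈ 41%. Any grade: odds 0.40/0.60 × 1.8 = 1.2, so 40% v 54.5%, power about 67%.

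**4. Simulation (20,000 or more replicates per scenario), range over the three distributions in each set.** The ordinal mean-score test uses scores 0-3.

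Set 1:

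| LAIV4 effect | Planned (grade ≥2) | Any grade | Mean score |
|---|---|---|---|
| +15 points, mild only | 5% | 68-75% | 33-43% |
| Odds ratio 1.8, all grades | 31-51% | (67% at 60/28/9/3%, step 3) | 57-72% |
| 10 points, mild to moderate | 51-70% | about 5% (proportion unchanged) | 15-19% |
| 10 points, none to moderate | 51-70% | not tabulated | 47-58% |

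Set 2 (40,000 replicates):

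| LAIV4 effect | Planned (grade ≥2) | Any grade | Mean score | van Elteren |
|---|---|---|---|---|
| +15 points, mild only | 5% | 68-75% | 33-40% | 46-61% |
| Odds ratio 2.0, all grades | 49-70% | 75-80% | 78-86% | 81-87% |
| 10 points, mild to moderate/severe | 48-64% | 5% | 19-22% | 8-15% |
| 10 points, none to moderate/severe | 47-64% | 36-41% | 53-60% | 52-55% |

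With no effect, every test rejects at about 5%.

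**5. Reading.** The planned test has no power beyond alpha for a mild-only excess and loses ground to ordinal tests for a shift across all grades. The any-grade test is equally blind to a move from mild to moderate/severe. Each covers the other's gap.

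**The case against.** The best defence is that the cut is a coherent safety threshold: grade 2 is where a reaction begins to interfere with activity. The plan describes every grade and tests those that affect the child, and mild nasal symptoms after LAIV are already acknowledged in the protocol. EO8 is one of ten exploratory objectives, with no power claim and no multiplicity control. All of that stands. It is the reason to keep the planned test, but it does not close the gap between the test and an outcome measure that has no grade limit.

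Two stronger readings are tempting, and the documents do not support them.

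- *Mild reactions are never compared.* SAP 8.3 h requires all four levels to be presented, so a mild excess would be visible in the table. Cough and wheezing, both on the protocol's list of LAIV reactions, are tested as yes/no in SO2 and again in EO2. What is missing is inference for mild reactions on the 12 EO8 items.
- *The cut throws away much of the power, so an ordinal test should replace it.* That depends on where the effect lies. For an upward move from mild, the planned test clearly beats the ordinal tests; for a move from none to the upper grades, it is similar or somewhat better or worse. With no grade rates in the documents, the direction of the power difference is itself an assumption.

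The mean-score test is also not the best answer to the mild-only case. A plain any-grade comparison has far more power there, and a common odds ratio would describe such an effect poorly.

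**Conclusion.** The point holds as a scope mismatch with a cheap remedy: EO8's only formal test starts at grade 2, while its objective and outcome measure cover any grade and the protocol points to mild reactions after LAIV.

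At 135 per arm, power for a 15-point mild-only excess is about 5%, against 68-75% with an any-grade test. For an odds ratio of 1.8 across grades it is about 31-51%, against 57-72% with a mean-score test. There is no general loss when the excess is confined to moderate/severe grades. These figures rest on assumed grade distributions and on reading the planned test as grade 2-3 against grade 0-1 on each child's worst grade. The SAP states neither the comparator nor the per-child summary outright. The matter is minor: it affects how one exploratory result can be interpreted and nothing in the primary or secondary analyses.

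**What to change.** In SAP 8.3 h:

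1. Define the analysis value as each participant's worst grade per item over Days 1-15, and state that the moderate/severe comparison is grade 2-3 against grade 0-1.
2. Keep the moderate/severe Mantel-Haenszel comparison as the clinically relevant summary. Do not replace it.
3. Add, for each of the 12 items, a Mantel-Haenszel comparison of any grade (1 or higher), stratified by asthma severity group, with the risk difference and 95% CI.
4. Optionally add a stratified mean-score or van Elteren test, labelled as supportive.

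This needs SAP wording and a few lines of code, and no new data. The downside of item 3 is up to 12 more unadjusted exploratory comparisons. Under no effect these would yield 12 × 0.05 = 0.6 extra nominal positives on average, so the estimates and intervals should lead the report rather than the p-values.
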